4.11.7 Strip Sign for Selected Laboratory Data

For selected laboratory test values that have been received with an operator sign as a part of the result $(>, \ge, <, \text{ or } \le)$, a process to strip the operator sign will be applied and the resulting numeric values will be used for data analysis. The raw value with operator will remain as such on the CRF (or in the electronic record) and in the database.

5. CHANGES OF ANALYSIS FROM THE PROTOCOL

1. The protocol text for the analysis of the primary efficacy variable specifies the null and alternative hypotheses in terms of 'control minus test' as follows:

The null hypothesis H_0 (given below) will be tested against the alternative hypothesis H_A ($\alpha = 0.025$, one-sided):

$$H_0$$
: $\mu_c - \mu_t \le -0.30\%$, H_A : $\mu_c - \mu_t > -0.30\%$

If the observed lower limit from a 2-sided 95% (or 1-sided 97.5%) CI for the difference in adjusted means is greater than -0.30%, then the test group will be considered to be non-inferior to the control group.

In order to be consistent with previous AZ studies of this nature and to aid comparisons across studies, this SAP refers to this in terms of 'test minus control' as follows:

The null hypothesis H_0 (given below) will be tested against the alternative hypothesis H_A ($\alpha = 0.025$, one-sided):

$$H_0$$
: $\mu_t - \mu_c \ge 0.30\%$, H_A : $\mu_t - \mu_c < 0.30\%$

If the upper limit of the 2-sided 95% CI is less than 0.30% then dapagliflozin or dapagliflozin plus saxagliptin will be considered to be non-inferior to glimepiride.

7. APPENDICES

7.1 Appendix I

7.1.1 List of Planned Tables

Demography

- 1. Patient disposition (All patients)
- 2. Analysis sets (All patients)
- 3. Relevant protocol deviations (Full analysis set)
- 4. Demographic characteristics (Randomised patients set)
- 5. Patient characteristics (Randomised patients set)
- 6. Diabetes-related and renal baseline characteristics (Randomised patients set)
- 7. Patient recruitment by country and centre (Randomised patients set)
- 8. Diabetes-related disease history (Randomised patients set)
- 9. Medical and surgical history (Randomised patients set)
- 10. All current medications (Safety analysis set)
- 11. All concomitant medications (Safety analysis set)

Extent of Exposure

- 12. Extent of exposure to Investigational Product (Safety analysis set)
- 13. Metformin dose at randomisation (Safety analysis set)
- 14. Dose levels of Glimepiride (Safety analysis set)
- 15. Dose levels of Glimepiride over time (Safety analysis set)
- 16. Dose titrations of Glimepiride (Safety analysis set)
- 17. Treatment interruptions (Safety analysis set)
- 18. Study treatment compliance (Safety analysis set)

Efficacy

- 19. Primary efficacy endpoint change from baseline in HbA1c at week 52 (Full analysis set)
- 20. Key Secondary efficacy endpoints (Full analysis set)
- 21. Change from baseline in HbA1c MMRM summary over time (Full analysis set)
- 22. Sensitivity analysis change from baseline in HbA1c at week 52 (Per Protocol analysis set)
- 23. Sensitivity analysis change from baseline in HbA1c at week 52, LOCF ANCOVA (Full analysis set)
- 24. Sensitivity analysis change from baseline in HbA1c at week 52 including all values regardless of use of rescue treatment or treatment discontinuation (Full analysis set)
- 25. Change from baseline in HbA1c Assessment of missing data patterns (Full analysis set)
- 26. Primary efficacy analysis MMRM summary (Full analysis set)
- 27. Change from baseline in HbA1c at week 52 by baseline HbA1c (Full analysis set)
- 28. Change from baseline in HbA1c at week 52 by age (Full analysis set)
- 29. Change from baseline in HbA1c at week 52 by gender (Full analysis set)
- 30. Change from baseline in HbA1c at week 52 by female age group (Full analysis set)
- 31. Change from baseline in HbA1c at week 52 by race (Full analysis set)
- 32. Change from baseline in HbA1c at week 52 by country (Full analysis set)

- 33. Change from baseline in HbA1c at week 52 by baseline eGFR (Full analysis set)
- 34. Change from baseline in weight MMRM summary over time (Full analysis set)
- 35. Change from baseline in FPG MMRM summary over time (Full analysis set)
- 36. Time to rescue Kaplan Meier estimates (Full analysis set)
- 37. Proportion meeting HbA1c criteria without confirmed hypoglycaemia at week 52 (Full analysis set)
- 38. Proportion meeting HbA1c criteria at week 52 (Full analysis set)
- 39. Proportion achieving individually agreed HbA1c targets at week 52 (Full analysis set)
- 40. Proportion with a HbA1c decrease >=1% with no weight gain (Full analysis set)
- 41. Time spent below HbA1c target (<7% and <7.5%) (Full analysis set)
- 42. Change in BMI from baseline to week 52 (LOCF) (Full analysis set)
- 43. Proportion with a weight reduction >=5% or a weight gain >=5% (Full analysis set)
- 44. Proportion with at least 1 episode of any hypoglycaemia (Full analysis set)
- 45. Change in waist circumference from baseline to week 52 (LOCF) (Full analysis set)
- 46. Change in systolic blood pressure from baseline to week 52 (MMRM) (Full analysis set)
- 47. Proportion with at least one episode of hypoglycaemia (symptomatic + blood glucose ≤70 mg/dL [3.9 mmol/L]) (Full analysis set)
- 48. Change from baseline over time in efficacy variables (observed values) (Full analysis set)

Exploratory

- 49. SF-36v2 scores and change from baseline (Full analysis set)
- 50. HFS-II worry scale mean score and change from baseline (Full analysis set)
- 51. IWQOL-Lite scores and change from baseline (Full analysis set)
- 52. Waist-to-hip ratio (Full analysis set)

Adverse Events

- 53. Overall adverse events summary (Safety analysis set) with data prior to rescue treatment only
- 54. Overall adverse events summary (Safety analysis set) including all data regardless of rescue
- 55. Adverse events by SOC and PT (Safety analysis set) with data prior to rescue treatment only
- 56. Adverse events by SOC and PT (Safety analysis set) including all data regardless of rescue
- 57. Adverse events by SOC and PT by age categories (Safety analysis set) including all data regardless of rescue
- 58. Adverse events by SOC and PT by gender (Safety analysis set) including all data regardless of rescue
- 59. Adverse events by SOC and PT by female age categories (Safety analysis set) including all data regardless of rescue
- 60. Adverse events by SOC and PT by race (Safety analysis set) including all data regardless of rescue
- 61. Most common adverse events (frequency >= 5% in any treatment group) (Safety analysis set) including all data regardless of rescue

- 62. Most common adverse events (frequency >= 2% in any treatment group) (Safety analysis set) including all data regardless of rescue
- 63. Adverse events by SOC and PT by maximum intensity (Safety analysis set) including all data regardless of rescue
- 64. Causally related Adverse events by SOC and PT (Safety analysis set) including all data regardless of rescue
- 65. Adverse events with an outcome of death by SOC and PT (Safety analysis set) including all data regardless of rescue
- 66. Adverse events with outcome of death key patient information (Safety analysis set) including all data regardless of rescue
- 67. Serious adverse events by SOC and PT (Safety analysis set) including all data regardless of rescue
- 68. Serious adverse events causally related to study medication by SOC and PT (Safety analysis set) including all data regardless of rescue
- 69. Adverse events leading to discontinuation of study medication by SOC and PT (Safety analysis set) including all data regardless of rescue
- 70. Adverse events of special interest, preferred terms
- 71. Adverse events of special interest, genital infection (Safety analysis set)
- 72. Adverse events of special interest, genital infection by gender (Safety analysis set)
- 73. Adverse events of special interest, antimicrobial treatment for genital infection by gender (Safety analysis set)
- 74. Adverse events of special interest, urinary tract infection (Safety analysis set)
- 75. Adverse events of special interest, urinary tract infection by gender (Safety analysis set)
- 76. Adverse events of special interest, antimicrobial treatment for urinary tract infection by gender (Safety analysis set)
- 77. Adverse events of special interest, renal impairment/failure (Safety analysis set)
- 78. Adverse events of special interest, volume depletion (Safety analysis set)
- 79. Adverse events of special interest, fracture (Safety analysis set)
- 80. Adverse events of special interest, hepatic disorder (Safety analysis set)
- 81. Adverse events of special interest, hypersensitivity reactions (Safety analysis set)
- 82. Adverse events of special interest, severe cutaneous adverse reactions (Safety analysis set)
- 83. Adverse events of special interest, gastroenteritis and upper respiratory tract infections (Safety analysis set)
- 84. Adverse events of special interest, decreased lymphocyte count (Safety analysis set)
- 85. Adverse events of special interest, pancreatitis (Safety analysis set)
- 86. Adverse events of special interest, all malignancies (Safety analysis set)
- 87. Adverse events of special interest, confirmed adjudicated hospitalisations for cardiac failure events (Safety analysis set)
- 88. Adverse events of special interest, cardiac failure (Safety analysis set)
- 89. Adverse events of special interest, DKA (Safety analysis set)
- 90. Non-serious adverse events occurring in greater than 5% of patients (Safety analysis set)
- 91. Hypoglycaemic events (Safety analysis set) with data prior to rescue treatment only

- 92. Hypoglycaemic events (Safety analysis set) including all data regardless of rescue
- 93. Hypoglycaemic events over time (Safety analysis set) with data prior to rescue treatment only
- 94. Hypoglycaemic events over time (Safety analysis set) including all data regardless of rescue

Laboratory Data, Vital Signs and ECG

- 95. Haematology and clinical chemistry laboratory variables over time (Safety analysis set)
- 96. Lipid parameters over time (Safety analysis set)
- 97. Marked Laboratory Abnormalities (Safety analysis set)
- 98. Proportion of subjects with elevated liver tests (Safety analysis set)
- 99. Patients with combined ALT or AST, and bilirubin, elevations individual patient data (Safety analysis set)
- 100. Sodium, Calcium Phosphorous and Magnesium, baseline to maximum value during treatment (Safety analysis set)
- 101. Sodium, Calcium Phosphorous and Magnesium, baseline to minimum value during treatment (Safety analysis set)
- 102. Urine Albumin to Creatinine Ratio shift table Baseline to Week 52 value (Safety analysis set
- 103. Urinalysis, baseline versus maximum value on treatment, shift table (Safety analysis set)
- 104. Vital signs variables over time (Safety analysis set)
- 105. ECG baseline versus week 52 (Safety analysis set)

7.1.2 List of Planned Figures

- 1. HbA1c adjusted mean change from baseline over time (Full analysis set)
- 2. Weight adjusted mean change from baseline over time (Full analysis set)
- 3. FPG adjusted mean change from baseline over time (Full analysis set)
- 4. HbA1c difference in adjusted mean change from baseline to week 52, Forest Plot (Full analysis set)
- 5. Weight difference in adjusted mean change from baseline to week 52, Forest Plot (Full analysis set)
- 6. Proportion of patients reporting at least one episode of confirmed hypoglycaemia from baseline to week 52, Forest Plot (Full analysis set)
- 7. Kaplan-Meier plot of Time to rescue(Full analysis set)
- 8. Kaplan-Meier plot of Time to discontinuation of study medication (Full analysis set)
- 9. HbA1c adjusted mean change from baseline over time by baseline HbA1c (Full analysis set)
- 10. Spaghetti plot of mean HbA1c over time (observed) grouped by last available visit on treatment Excluding data after rescue (Full analysis set)
- 11. Most common adverse events (>=2%), by preferred term, dot plot showing relative risk (Safety analysis set)

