Visit 2 (Randomisation/Baseline) should be performed within 14 days after Enrolment visit, when laboratory results from Visit 1 are available. in patients that do not have a recent HbA1c value (within 30 days)

donce a patient is randomised at Visit 2, all visits should be scheduled relative to Visit 2.

'An abbreviated informed consent form will be signed at Screening visit. Review of concomitant medications includes over the counter drugs and herbal/nutritional therapies

Specifications of clinical chemistry laboratory parameters are detailed in CSP Section 5.2.1.3. Visits 1 and 8 to 11 have the same parameters; Visits 2, 12, and 13 have the same parameters; and no clinical chemistry is performed at Visits 3 through 7. CrCl and eGFR will be calculated at all visits.

'Serum lipid panel will include LDL-cholesterol, HDL-cholesterol, triglycerides, and total cholesterol.

Hepatitis panel includes hepatitis B viral antibody IgM, Hepatitis B surface antigen, and hepatitis C virus antibody.

Visit windows for the analysis of efficacy and safety variables are described in detail in Section 4.11.2.

The study will be run at approximately 250 sites mainly in Germany and European Union (EU). Approximately 930 patients (310 patients per treatment group) are planned for randomisation to ensure that at least 290 patients per treatment group are evaluable in the Full Analysis Set (assuming 5% exclusion rate from Full Analysis Set). Assuming however that approximately 30% of screened patients will fail the entry criteria, a total of (approximately) 1329 patients will be enrolled.

Sites will be allowed to perform a pre-study screening assessment (at Week -3) prior to enrolment visit to screen for HbA1c criteria. All potentially eligible patients will be enrolled, provide informed consent, undergo screening for all applicable inclusion/exclusion criteria, and submit laboratory samples at Enrolment (Visit 1, 2 weeks prior to randomisation). Patients should be treated with a stable, maximum tolerated dose of metformin monotherapy (≥1500 mg/day) for at least 8 weeks prior to Enrolment, and remain on the same type and dose of metformin therapy for the duration of the study as the background therapy for all treatment arms, as indicated in Section 1.2.2.

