1.3 Number of patients

To demonstrate non-inferiority of dapagliflozin plus metformin or dapagliflozin plus saxagliptin plus metformin to glimepiride plus metformin for changes from baseline to week 52 in HbA1c within a non-inferiority margin of 0.30% - assuming a standard deviation 1.0%, and at a 1-sided significance level of 0.025 - 290 evaluable patients will be needed in each treatment group to provide approximately 95% power (given a true difference of zero between dapagliflozin or dapagliflozin plus saxagliptin and glimepiride). The non-inferiority margin of 0.3% as well as a common standard deviation of 1.0% were selected based on information from earlier, similarly designed studies. Assuming that 5% of patients do not have a post-baseline assessment, a total of approximately 930 patients (310 patients per treatment arm) need to be randomised. Moreover, if 30% of screened patients fail to meet screening criteria, a total of 1329 patients need to be screened.

A hierarchical testing procedure will be followed to control type 1 error rate of 0.05. Dapagliflozin plus saxagliptin plus metformin will be tested for non-inferiority first. If dapagliflozin plus saxagliptin plus metformin is non-inferior to glimepiride plus metformin then dapagliflozin plus metformin will be tested for non-inferiority.

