2.3 Full Analysis Set

The Full Analysis Set will include all randomised patients who receive at least one dose of study medication and who have a non-missing baseline value and at least one post-baseline efficacy value (i.e., HbA1c, FPG, weight). Patients will be analysed according to the treatment they were originally assigned (based on the ITT principle).

The Full Analysis set will be used for addressing the non-inferiority claim for the primary efficacy objective and also for the analysis of all secondary objectives.

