7.4 Appendix IV – Missing data pattern for HbA1c

Table 16. Assessment of missing data patterns by visit and treatment group (Full analysis set)

Visit	Change from Baseline in HbA1c Assessments	DAPA + MET $(N = XXX)$	DAPA + SAXA + MET $(N = XXX)$	GLIM + MET $(N = XXX)$
Week X	Available at Week X	XXX (XX.X%)	XXX (XX.X%)	XXX (XX.X%)
	No baseline assessment available	X (X.X%)	X (X.X%)	X (X.X%)
	Missed Visit	X (X.X%)	X (X.X%)	X (X.X%)
	Lost to Follow-up	X (X.X%)	X (X.X%)	X (X.X%)
	Discontinued Study Medication	X (X.X%)	X (X.X%)	X (X.X%)
	Rescued	X (X.X%)	X (X.X%)	X(X.X%)
	Cumulative Patients Excluded:			
	Primary Efficacy Analysis	X (X.X%)	X (X.X%)	X (X.X%)
	Sensitivity Analysis*	X (X.X%)	X (X.X%)	X(X.X%)
Week Y	Available at Week Y	XXX (XX.X%)	XXX (XX.X%)	XXX (XX.X%)
	No baseline assessment available	X (X.X%)	X (X.X%)	X (X.X%)
	Missed Visit	X (X.X%)	X (X.X%)	X (X.X%)
	Lost to Follow-up	X (X.X%)	X (X.X%)	X (X.X%)
	Discontinued Study Medication	X (X.X%)	X (X.X%)	X (X.X%)
	Rescued	X (X.X%)	X (X.X%)	X(X.X%)
	Cumulative Patients Excluded:			
	Primary Efficacy Analysis	X (X.X%)	X (X.X%)	X (X.X%)
	Sensitivity Analysis*	X (X.X%)	X (X.X%)	X (X.X%)

Missed Visit = Patient has an HbA1c at a visit before and an HbA1c at a visit after the Missed Visit.

Lost to Follow-up (e.g., Right Censored) = Patient has an HbA1c at a visit before but no HbA1c assessments after the visit.

Discontinued Study Medication = Patient has discontinued study medication prior to that visit (will result in exclusion from Primary Efficacy analysis; may or may not have an HbA1c available).

Rescued = Patient has received rescue medication prior to that visit (will result in exclusion from Primary Efficacy analysis; may or may not have an HbA1c available).

Cumulative number (%) patients excluded from the primary efficacy analysis is the distinct patients within (LTFU + Discontinued Study Med + Rescued + No baseline available)

Cumulative number (%) patients excluded from the sensitivity analysis is the distinct patients within (LTFU + No baseline available)

^{*} Sensitivity analysis re-running MMRM including all values regardless of use of rescue medication or treatment discontinuation

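### Figure 8 plots time to discontinuation of study medication on the Full Analysis Set, so dosed patients who stop and are never measured again cannot appear on the curve

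*SAP*

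**What the plan says.** SAP section 7.1.2 lists the figure as "8. Kaplan-Meier plot of Time to discontinuation of study medication (Full analysis set"). Section 4.10 also lists this curve, but names no population for it.

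Section 2.3 defines the set: "The Full Analysis Set will include all randomised patients who receive at least one dose of study medication", subject to two further conditions, a baseline value and "at least one post-baseline efficacy value (i.e., HbA1c, FPG, weight"). It assigns the set to the primary efficacy objective and the secondary objectives. Time to discontinuation is not among the efficacy variables in sections 3.1 to 3.3.

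The plan expects some patients to fall outside the set. Section 1.3 writes "Assuming that 5% of patients do not have a post-baseline assessment"; section 1.2 puts the same allowance as "assuming 5% exclusion rate from Full Analysis Set".

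Other outputs on study medication use the Safety Analysis Set, which needs only randomisation and one dose (section 2.5). They are extent of exposure (4.7.2.1), interruptions (4.7.2.2), compliance (4.7.4) and adverse events leading to discontinuation (4.9.3, planned table 69).

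**The concern.** A time-to-discontinuation curve should start from everyone who began treatment. Here, entry to the plotted set depends on something that happens after randomisation and is linked to the plotted event. A patient who takes a few doses, stops and does not return has a discontinuation time but no post-baseline value, so is in neither the numerator nor the denominator.

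The loss falls at the start of the curve. If it differs between arms, the curves can separate, or fail to separate, because of who was admitted to the set. Figure 8 would also have a different denominator from the exposure table and from planned table 69, so the outputs would not reconcile directly.

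**Working it through.** **The plan's own figures.** With margin 0.30%, SD 1.0%, true difference 0, one-sided 0.025 and 95% power (section 1.3), the normal formula gives 2 × (1.960 + 1.645)² × 1.0² / 0.30² ≈ 289 per arm, against the stated 290. Allowing for 5% loss, 290 / 0.95 = 305.3, so 306, against the stated 310. The sample size reproduces.

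**Patients the 5% stands for.** 930 × 0.05 = 46.5, or 310 × 0.05 = 15.5 per arm. The curve would start from about 310 − 15.5 = 294.5 per arm.

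**Effect on the curve.** Let c be the true proportion of dosed patients who discontinue by Week 52, and e the proportion who stop with no post-baseline value. Ignoring censoring, and with every patient counted in e also counted in c:

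- proportion shown on the Full Analysis Set = (c − e) / (1 − e)
- shortfall = c − (c − e) / (1 − e)

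The SAP gives no value for c, so 10%, 15% and 20% are assumptions. Setting e = 5% treats the whole allowance as dosed early dropouts.

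| e | c = 10% | c = 15% | c = 20% | Shortfall (points) |
|---|---|---|---|---|
| 5% | 0.05/0.95 = 5.3% | 0.10/0.95 = 10.5% | 0.15/0.95 = 15.8% | 4.7, 4.5, 4.2 |
| 1% | 0.09/0.99 = 9.1% | 0.14/0.99 = 14.1% | 0.19/0.99 = 19.2% | 0.9, 0.9, 0.8 |
| 0 | 10% | 15% | 20% | 0 |

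**Unequal early loss (illustration, all values assumed).** Two arms both truly lose 15%, but e is 8% in one and 2% in the other:

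- first arm: (0.15 − 0.08) / 0.92 = 7.6%
- second arm: (0.15 − 0.02) / 0.98 = 13.3%

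The plotted difference of 5.7 points comes entirely from the choice of population. In the first arm the shortfall is 15 − 7.6 = 7.4 points, so the 4-to-5-point figure holds only when the 5% is spread evenly over the arms.

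**The case against.** **The patients are reported elsewhere.** A reader might infer that the earliest dropouts are hidden from the report. They are not:

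- Section 4.7.1.1 and planned table 1 give disposition for all patients, with reasons.
- Planned table 2 gives the analysis sets for all patients.
- Listing 7 gives exclusions from the analysis sets.
- Section 4.7.2.1 bands days of exposure by arm in the Safety Analysis Set, starting with days 1–6 and 7–14, so early timing is available too.

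This objection stands. What remains is that figure 8 itself does not show these patients.

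**Most early stoppers may stay in the set.** A reader might infer that anyone stopping before Week 2 is lost. Section 2.3 asks for one post-baseline value, not continued treatment. HbA1c, FPG and weight are all taken from Week 2, and the note to the study plan (Table 1) requires early-termination procedures for patients who terminate the study early. A patient who stops on day 5 and attends either visit is on the curve. This also stands, and it limits the point to patients never measured again.

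**The 5% is a ceiling.** It is a planning allowance, and section 1.2 words it as the overall exclusion rate, which can include never-dosed patients and those without a baseline. Moving to the Safety Analysis Set would not bring back never-dosed patients, and they have no time on drug to plot.

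**The missing-data table.** The shell in Appendix IV, "Table 16. Assessment of missing data patterns by visit and treatment group (Full analysis set"), and its entry in the table list, "25. Change from baseline in HbA1c Assessment of missing data patterns (Full analysis set"), use the same set, so a reader might extend the criticism to them. Section 4.6.2 uses this table to explore the assumption behind the primary MMRM, which is itself run on the Full Analysis Set, so the choice is defensible. Nor does its row for patients without a baseline assessment show that it was built for a wider set. Section 2.3 requires "who have a non-missing baseline value and at least one post-baseline efficacy value" without saying that the baseline value must be HbA1c, so a patient in the set could lack a baseline HbA1c.

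**Conclusion.** The point holds for figure 8. The curve leaves out dosed patients who stop and are never measured again, and nothing in the SAP requires the Full Analysis Set for this display.

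The understatement is about 4 to 5 percentage points at the upper end. That needs the full 5% to be dosed early dropouts, spread evenly over the arms, and an assumed true 52-week discontinuation of 10–20%. It is under 1 point at 1% affected and zero if nobody is. A distorted comparison between arms needs unequal early loss, on which the SAP gives no figure.

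A reader might go further and infer that the non-inferiority result is affected. The documents do not support that: no estimate, confidence interval, test or sample size uses figure 8. This is a fault in the population chosen for one display.

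**What to change.** Change the population of figure 8 in section 7.1.2 to the Safety Analysis Set, and state it beside the curve in section 4.10. The figure then shares its denominator with the exposure, interruption, compliance and discontinuation-AE outputs.

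Table 16 and planned table 25 may stay as they are. An optional footnote could give, by arm, the number of randomised patients outside the Full Analysis Set, with reasons.

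The cost is one population label. There are two consequences. Reported discontinuation may look slightly higher. Patients would also be shown by treatment received, as section 2.5 sets out, which should be said on the figure.
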